10.8. Biomarkers

Exploratory analysis will be conducted on archived tumor tissue for loss of PTEN and PIK3CA mutations (Section 5.2).

11. SAFETY REPORT AND ANALYSES

11.1. Safety Analyses

Safety assessments will consist of monitoring and recording protocol-defined AEs and SAEs; measurement of protocol specified hematology, clinical chemistry, and urinalysis variables;

CONFIDENTIAL

STUDY DRUG: Orteronel

SCRI INNOVATIONS STUDY NUMBER: BRE 203

DATE OF PROTOCOL: Version 3.0 30 October 2013

Page 56 of 80

measurement of protocol-specified vital signs; and other protocol-specified tests that are deemed critical to the safety evaluation of the study drug.

Investigators must report SAEs and follow-up information to their responsible Institutional Review Board (IRB) according to the policies of the responsible IRB.

11.2. Adverse Events

11.2.1. Definitions of Adverse Events

An AE is the development of an undesirable medical condition, or the deterioration of a pre-existing medical condition following or during exposure to a medicinal product, whether or not considered causally related to the product.

An undesirable medical condition can be symptoms (e.g., nausea, chest pain), signs (e.g., tachycardia, enlarged liver), or the abnormal results of an investigation (e.g., laboratory findings).

11.2.2. Recording of Adverse Events

All AEs of any patient during the course of the trial will be reported in the case report form, and the investigator will give his or her opinion as to the relationship of the AE to study drug treatment (i.e., whether the event is related or unrelated to study drug administration). If the AE is serious, it should be reported immediately to SCRI Innovations Safety Department. Other untoward events occurring in the framework of a clinical trial are also to be recorded as AEs (i.e., AEs that occur prior to assignment of trial treatment that are related to a protocol-mandated intervention, including invasive procedures such as biopsies, medication washout, or no treatment run-in).

All AEs regardless of seriousness or relationship to orteronel treatment (called trial treatment), spanning from the initiation of trial treatment, until 30 calendar days after discontinuation or completion of protocol-specific treatment as defined by the protocol for that patient, are to be recorded in the eCRF.

11.2.3. Handling of Adverse Events

All AEs resulting in discontinuation from the trial should be followed until resolution or stabilization. Patients must be followed for AEs for 30 calendar days after discontinuation or completion of protocol-specific treatment (e.g., chemotherapy, radiation, oral medications, targeted therapy, and surgery). All new AEs occurring during this period must be reported and followed until resolution unless, in the opinion of the investigator, the AE or laboratory abnormality/ies are not likely to improve because of the underlying disease. In this case, the investigators must record his or her reasoning for this decision in the patient's medical record and as a comment on the eCRF. After 30 days of completion of protocol-specific treatment or discontinuation, only AEs, SAEs, or deaths assessed by the investigator as treatment related are to be reported.

CONFIDENTIAL

STUDY DRUG: Orteronel

SCRI INNOVATIONS STUDY NUMBER: BRE 203

DATE OF PROTOCOL: Version 3.0 30 October 2013

11.3. Serious Adverse Events

11.3.1. Definitions of Serious Adverse Events

The definitions of SAEs are presented in this section. The Principal Investigator is responsible for ensuring that all staff members involved in the study are familiar with the content of this section.

An SAE or reaction is defined as any untoward medical occurrence that at any dose:

- Results in death
- Is immediately life-threatening (Refers to an AE in which the patient was at risk of death at the time of the event. It does not refer to an event that hypothetically might have caused death, if it were more severe.)
- Requires at least a 24-hour in-patient hospitalization or prolongation of existing hospitalization
- Results in persistent or significant disability/incapacity (Disability is defined as a substantial disruption of a person's ability to conduct normal life functions.)
- Is a congenital anomaly/birth defect
- Is a medically important event.

Medical and scientific judgment should be exercised in deciding whether expedited reporting is appropriate in other situations, such as important medical events that may not be immediately life-threatening or result in death or hospitalization, but may jeopardize the patient or may require intervention to prevent one of the other outcomes listed in the previous definition. These should also usually be considered serious. Examples of such events are intensive treatment in an emergency room or at home for allergic bronchospasm; blood dyscrasias or convulsions that do not result in hospitalization; or development of drug dependency or drug abuse. Progression of malignancy (including fatal outcomes), if documented by use of appropriate method (for example, as per RECIST criteria for solid tumors), should not be reported as an SAE.

Treatment within or admission to the following facilities is not considered to meet the criteria of "in-patient hospitalization" (although if any other SAE criteria are met, the event must still be treated as an SAE and immediately reported):

- Emergency Department or Emergency Room
- Outpatient or same-day surgery units
- Observation or short-stay unit
- Rehabilitation facility
- Hospice or skilled nursing facility
- Nursing homes, Custodial care or Respite care facility

CONFIDENTIAL

STUDY DRUG: Orteronel

SCRI INNOVATIONS STUDY NUMBER: BRE 203

DATE OF PROTOCOL: Version 3.0 30 October 2013

Hospitalization during the study for a pre-planned surgical or medical procedure (one which was planned prior to entry in the study), does not require reporting as a SAE to the SCRI Innovations Safety Department.

11.3.2. Serious Adverse Event Reporting by Investigators

It is important to distinguish between “serious” and “severe” AEs, as the terms are not synonymous. Severity is a measure of intensity; however, an AE of severe intensity need not necessarily be considered serious. For example, nausea which persists for several hours may be considered severe nausea, but may not be considered an SAE. On the other hand, a stroke which results in only a limited degree of disability may be considered only a mild stroke, but would be considered an SAE. Severity and seriousness should be independently assessed when recording AEs on the eCRF and SAEs on the SAE Report Form.

Adverse events classified by the treating investigator as serious require expeditious handling and reporting to SCRI Innovations in order to comply with regulatory requirements. Serious AEs occurring during the course of the study (spanning from the initiation of orteronel treatment through 30 days following the last dose of study medication) will be reported by the Investigator to SCRI Innovations Safety Department via fax or email, and are to be recorded in the eCRF. If a patient experiences an SAE after signing the informed consent, but prior to receiving study drug, the event does not need to be recorded as an SAE unless the investigator feels the event may have been caused by a protocol procedure. The SCRI Innovations Safety Department must be notified of all SAEs, regardless of causality, within 1 business day of the first knowledge of the event by the treating physician or research personnel.

To report an SAE, the SAE Report Form should be completed with the necessary information. All SAEs occurring from the signing of consent until 30 calendar days of last study treatment must be reported to the Sponsor as SAEs on the SAE Report and followed until resolution (with autopsy report if applicable).

Deaths and other SAEs occurring >30 calendar days after last study treatment that are deemed ‘possibly’ or ‘probably’ related to orteronel must be reported as SAEs on the SAE Report within 1 business day of first knowledge of the event by the treating physician or research personnel (with an autopsy report if available).

Deaths occurring >30 calendar days after last study treatment and not attributed to study treatment (e.g., disease progression) need not be reported as SAEs, but simply captured on the appropriate eCRF.

The SAE report should be sent to the SCRI Innovations Safety Department via fax or e-mail using the contact information listed below:

SCRI Innovations Safety Department

[contact]

Safety Dept. Email: [contact]

Transmission of the SAE report should be confirmed by the site personnel submitting the report.

Follow-up information for SAEs and information on non-serious AEs that become serious should also be reported to SCRI Innovations Safety Department as soon as it is available; these reports

CONFIDENTIAL

STUDY DRUG: Orteronel

SCRI INNOVATIONS STUDY NUMBER: BRE 203

DATE OF PROTOCOL: Version 3.0 30 October 2013

should be submitted using the SCRI Innovations SAE Report Form. The detailed SAE reporting process will be provided to the sites in the SAE reporting guidelines contained in the study reference manual.

Investigators must report SAEs and follow-up information to their responsible Institutional Review Board (IRB) according to the policies of the responsible IRB.

11.3.3. Sponsor SAE Reporting Requirements

SCRI Development Innovations, LLC will forward SAE and pregnancy information to Millennium Pharmacovigilance within 1 business day of SCRI Innovations Safety Department personnel becoming aware of the SAE.

Millennium Pharmacovigilance
SAE and Pregnancy Reporting Contact Information:
North America PPD, Inc.
Safety and Medical Management, US
[contact]
Hotline number (available 24/7): [name]

The Sponsor (SCRI Development Innovations, LLC) is responsible for reporting relevant SAEs to the competent authority, other applicable regulatory authorities, and participating investigators, in accordance with ICH guidelines, FDA regulations, and/or local regulatory requirements.

11.4. Recording of Adverse Events and Serious Adverse Events

Investigators should use correct medical terminology/concepts when recording AEs or SAEs on the SAE Report Forms and AE eCRF. Avoid colloquialisms and abbreviations.

All AEs, including those that meet SAE reporting criteria, should be recorded on the AE eCRF; AEs that meet the definition of an SAE should additionally be reported following the procedures noted in Section 11.3.2.

11.4.1. Diagnosis versus Signs and Symptoms

All AEs should be recorded individually in the patient's own words (verbatim) unless, in the opinion of the Principal Investigator or designated physician, the AEs constitute components of a recognized condition, disease, or syndrome. In the latter case, the condition, disease, or syndrome should be named rather than each individual sign or symptom. If a constellation of signs and/or symptoms cannot be medically characterized as a single diagnosis or syndrome at the time of reporting, each individual event should be recorded as an AE or SAE as appropriate on the relevant form(s) (SAE Report Form and/or AE eCRF). If a diagnosis is subsequently established, it should be reported as follow-up information is available. If a diagnosis is determined subsequent to the reporting of the constellation of symptoms, the signs/symptoms should be updated to reflect the diagnosis.

11.4.2. Persistent or Recurrent Adverse Events

A persistent AE is one that extends continuously, without resolution, between patient evaluation time points. Such events should only be recorded once on the SAE Report Form and/or the

CONFIDENTIAL

STUDY DRUG: Orteronel

SCRI INNOVATIONS STUDY NUMBER: BRE 203

DATE OF PROTOCOL: Version 3.0 30 October 2013

AE eCRF. If a persistent AE becomes more severe or lessens in severity, it should be recorded on a separate SAE Report Form and/or AE eCRF.

A recurrent AE is one that occurs and resolves between patient evaluation time points, and subsequently recurs. All recurrent AEs should be recorded on an SAE Report Form and/or AE eCRF.

11.4.3. Abnormal Laboratory Values

Any Grade 3 or 4 laboratory abnormalities or any clinically significant Grade 1 or 2 hematology or biochemistry laboratory value(s) should be recorded as an AE. If an abnormal laboratory value or vital sign is associated with clinical signs and/or symptoms, the sign or symptom should be reported as an AE, and the associated laboratory value or vital sign should be considered additional information that must be collected on the relevant eCRF. If the laboratory abnormality is a sign of a disease or syndrome, only the diagnosis needs to be recorded on the SAE Report Form or AE eCRF.

11.4.4. Deaths

For this protocol, observation of the clinical and laboratory AEs produced by orteronel is the primary efficacy endpoint.

Deaths that occur during the protocol-specified AE reporting period that are attributed by the investigator solely to progression of disease will be recorded on the “Study Discontinuation” eCRF. All other on-study deaths, regardless of attribution, will be recorded on an SAE Report and expeditiously reported to the SCRI Innovations Safety Department.

When recording a SAE with an outcome of death, the event or condition that caused or contributed to the fatal outcome should be recorded as the single medical concept on the SAE report and Adverse Event page of the eCRF. If the cause of death is unknown and cannot be ascertained at the time of reporting, record “Death NOS” on the eCRF Adverse Event page.

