10.6. Efficacy Measures

The primary efficacy endpoints for both Cohort 1 and Cohort 2 are the RR and DCR.

Secondary efficacy endpoints are PFS and OS.

Efficacy analyses will include all patients in the ITT population.

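### Sections 11.3.1 and 11.4.4 set different tests for a death attributed to progression, so one without documented progression is an SAE under the first and not under the second

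*Combined protocol and SAP*

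**What the plan says.** Section 11.3.1 lists "Results in death" among the criteria that make an event serious. It then makes an exception for progression of malignancy, fatal outcomes included, which "if documented by use of appropriate method (for example, as per RECIST criteria for solid tumors), should not be reported as an SAE".

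Section 11.3.2 sets the reporting duty: "All SAEs occurring from the signing of consent until 30 calendar days of last study treatment must be reported to the Sponsor". The Safety Department must hear of every SAE within 1 business day, whatever its cause. Relief for deaths not attributed to treatment applies only beyond 30 days after the last dose. Under Section 11.3.3 the sponsor passes SAEs to the supplier's pharmacovigilance group within 1 business day of its Safety Department learning of them.

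Section 11.4.4 gives its own rule for deaths inside the reporting period. Those "attributed by the investigator solely to progression of disease will be recorded on the" Study Discontinuation eCRF. Then: "All other on-study deaths, regardless of attribution, will be recorded on an SAE Report", with expeditious reporting to the Safety Department.

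The same section opens by saying that "observation of the clinical and laboratory AEs produced by orteronel is the primary efficacy endpoint". Section 10.6 says: "The primary efficacy endpoints for both Cohort 1 and Cohort 2 are the RR and DCR".

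**The concern.** The exemption in 11.4.4 depends on the investigator's opinion of cause. The exemption in 11.3.1 depends on evidence that the disease progressed. Neither section refers to the other on this point, so two sites can classify the same death differently and each can cite the protocol.

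What is at stake is the speed and independence of safety review. A death on an SAE Report reaches the Safety Department and then the supplier within days. A death entered only on the discontinuation form does not trigger those steps. The distinction matters here because Section 1.2.2.1 lists hepatotoxicity and adrenal insufficiency as identified risks, and the severe picture in Table 8 (Grade 3 fatigue, anorexia, prostration, hypotension) can resemble decline from metastatic disease. Attribution without documented progression is the case where a second look is most useful.

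**Working it through.** No figure in the plan bears on this point, so the check is a comparison of the texts.

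**Step 1. Apply each section to the possible cases, for a death within the reporting period.**

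| Investigator's attribution | Progression documented? | Under 11.3.1 | Under 11.4.4 |
|---|---|---|---|
| Solely progression | Yes | Exempt | Exempt |
| Solely progression | No | SAE | Exempt |
| Not solely progression | Either | SAE, through the event that caused or contributed to death | SAE Report |

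The sections disagree only in the second row.

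**Step 2. See whether another section resolves that row.** Section 11.3.2 does not. Its duty covers all SAEs up to 30 days after last treatment, and its relief for unrelated deaths starts only after that. Section 11.4 sends events that meet the SAE definition to the 11.3.2 procedures, but 11.4.4 then gives a specific instruction for deaths without repeating or citing the documentation condition.

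**Step 3. See whether the second row can occur.** Cycles last 28 days (Section 7.4), and the first scheduled on-study CT is on Day 1 of Cycle 3 (Section 7.4.2). That is after 2 × 28 = 56 days, before visit windows. Until then no scheduled scan exists to document progression. The lead-in review, after 4 weeks of treatment in 6 patients, falls inside this period. The gap can also arise later: bone-only disease is eligible, yet bone scans are done only if clinically indicated, and the end-of-treatment CT is required only when the last assessment was more than 8 weeks earlier and progression is not already documented.

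**Step 4. Trace the consequence.** Under 11.4.4 a second-row death is recorded on an eCRF, and so is captured. It does not by itself start the 1-business-day notice in 11.3.2 or the forwarding in 11.3.3.

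**Step 5. Compare the endpoint statements.** RR and DCR are the primary objectives in 2.1 and the primary efficacy endpoints in 10.6. Sections 10.3 and 10.4 build the sample size and the stopping and success rules on response. Section 10.7 makes toxicity the safety endpoint, and 2.2 makes safety a secondary objective. The opening sentence of 11.4.4 stands alone against all of these.

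**The case against.** The strongest reply is that the two sections can be followed together. Section 11.4 points back to the SAE definition, which contains the documentation condition, and 11.4.4 does not say that it overrides it. On that reading a death is exempt only if attribution is sole and progression is documented, and the fault is a missing cross-reference. This is a reasonable way to harmonise the text, but the text does not say it. A site that follows 11.4.4 as written leaves out a report that 11.3.1 and 11.3.2 require.

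A reader might infer that fatal toxicity would be hidden or under-counted. The documents do not support that:

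- The 11.4.4 exemption is confined to deaths attributed solely to progression. Any suspected drug contribution, or an unknown cause, puts the death on an SAE Report.
- Preceding events have their own reporting routes: all AEs regardless of relationship (11.2.2), Grade 3 or 4 laboratory abnormalities (11.4.3), and hospitalizations over 24 hours (11.4.5). Liver tests are part of the metabolic profile drawn each cycle, and weekly in Cycle 1 for lead-in patients. These routes are not complete, because 11.4.8 keeps symptoms of metastasis out of AE reporting, but they are substantial.
- The death still counts for PFS and OS.

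A reader might also put a number on it, for instance by assuming that 2–5% of the 86 patients die before the first scheduled scan (86 × 0.02 = 1.7; 86 × 0.05 = 4.3). The documents give no early-death rate, and entry requires a life expectancy of at least 3 months. Such a count would be at most the deaths in that period whose SAE status could be unclear, not a measure of missed toxicity. Nor does the scan date define who is affected: RECIST is only an example of an appropriate method, and clinical examination or imaging done when indicated may document progression earlier.

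Lastly, a reader might take the endpoint sentence as undermining the two-stage design. It does not, because the rules in 10.4 are stated explicitly in terms of response.

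**Conclusion.** The inconsistency is real and narrow. It concerns deaths within the adverse-event reporting period that the investigator attributes solely to progression and for which progression has not been documented. For those deaths the protocol gives two answers on SAE status. The loss is expedited review and forwarding, not the record of the death.

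The number of such deaths cannot be derived from the documents, and the conclusion does not depend on it. It rests on reading 11.4.4 as written, without importing a condition that the section does not state. It deserves correction because it concerns safety capture and the remedy is small. No efficacy analysis is affected.

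The endpoint sentence is a plain editorial error with no operational effect and would not merit a separate point.

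**What to change.** Reconcile the two sections. The simplest way is to carry the existing 11.3.1 condition into 11.4.4, along these lines:

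*A death in the AE reporting period goes on the Study Discontinuation eCRF alone only when the investigator attributes it solely to disease progression and that progression has been documented as Section 11.3.1 requires. Every other death in the period goes on an SAE Report under Section 11.3.2.*

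If the sponsor intends attribution alone to be enough, 11.3.1 has to be changed to say so, but that gives up the safeguard it now contains.

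As an editorial correction in the same section, delete the sentence naming AEs as the primary efficacy endpoint, or replace it with a reference to RR and DCR in Section 10.6.

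The cost is two sentences in an amendment and possibly a few extra SAE reports. Sample size, stopping rules and analyses are unchanged.

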11.4.5. Hospitalization, Prolonged Hospitalization, or Surgery

Any AE that results in hospitalization of >24 hours or prolonged hospitalization should be documented and reported as an SAE unless specifically instructed otherwise in this protocol. There are some hospitalization scenarios that do not require reporting as an SAE when there is no occurrence of an AE (see Section 11.3.2).

11.4.6. Pre-Existing Medical Conditions

A pre-existing medical condition is one that is present at the start of the study. Such conditions should be recorded on the General Medical History eCRF. A pre-existing medical condition should be recorded as an AE or SAE only if the frequency, severity, or character of the condition worsens during the study. When recording such events on an SAE Report Form and/or AE eCRF, it is important to convey the concept that the pre-existing condition has changed by including applicable descriptors.

11.4.7. Pregnancy, Abortion, or Birth Defects/Congenital Anomalies

Pregnancy, abortion, birth defects, and congenital anomalies are events of special interest. Please refer to Section 11.5 for specific instructions.

CONFIDENTIAL

STUDY DRUG: Orteronel

SCRI INNOVATIONS STUDY NUMBER: BRE 203

DATE OF PROTOCOL: Version 3.0 30 October 2013

11.4.8. New Cancers

The development of a new primary cancer should be regarded as an AE and will generally meet at least one of the serious criteria (see Section 11.3). New primary cancers are those that are not the primary reason for the administration of the study treatment and have developed after the inclusion of the patient into the study. They do not include metastases of the original cancer. Symptoms of metastasis or the metastasis itself should not be reported as an AE/SAE, as they are considered to be disease progression.

